8.12. Piloting, standardization and quality control

The study instruments will be piloted by experienced data collectors, and their feedback incorporated to finalize the questionnaires. SOPs for data collection and quality assurance will be developed. The IOA team conducting anthropometric measurements will be rigorously standardised in accordance with the established protocols. The IOA team will also be standardised on all the questionnaires, assessments and scales, including the BBAT, PSBI assessment, EPDS, MIBS, etc. The study coordinator will directly supervise the IOA team – random spot checks will be made for 10% of all visits.

The SESS team will be standardised on newborn weighing, support of breastfeeding initiation through SSC during the first hour, eligibility screening and enrolment procedures, and supporting facility nurses in the provision of essential newborn care counselling. Hospital nurses, who are responsible for measuring the birth weight of newborns, will be trained in the standardized measurement of birth weight. The SESS team will oversee the measurement of birth weight by the hospital nurses for all newborns whose mothers have been consented for screening. The same digital infant weighing scale (Seca 334 or equivalent) will be used across all study centres for each time point of data collection from birth to age 28 days. A dedicated team lead will supervise the SESS team and will conduct random spot-checks for 10% of interactions in the labour room and wards.

The KMC team will be trained and mentored by experienced workers on supporting mothers in providing prolonged KMC to their babies. A dedicated team lead will supervise the KMC team and will conduct daily facility visits to ensure quality and standardised delivery of the intervention.

8.13. Data management

Data management will be a crucial aspect of our study, ensuring the accuracy, integrity, and confidentiality of the collected data. All study data will be collected on electronic case report forms on Android-enabled devices using a common data management platform. It will be stored in a secure, cloud-based password-protected database, accessible only to authorized personnel. We will

implement strict data quality control procedures, including range checks, consistency checks, and periodic audits, to minimize data entry errors and ensure data validity. All electronic data will be backed up regularly, with copies stored in a separate secure location. Consent forms and any other physical data will be stored in a locked cabinet in a secure area, with access restricted to authorized study personnel only. The data will be anonymized and coded to maintain participant confidentiality. The data management team will collate reports based on data received from all the study sites, conduct statistical analysis and support data monitoring. Each site will also review its own data for quality purposes, and present findings during monthly steering committee review meetings. Any requests for data access for secondary analyses will be reviewed by the study team, and approval will be contingent upon ethical considerations and relevance to the study objectives.

8.14. Statistical analysis

The detailed analysis plan based on the following high-level plan will be finalized a priori before initiating any analysis of the study data. Statistical analysis will be conducted using R or STATA.

Baseline characteristics will be compared between the intervention and control groups using independent samples t-tests for continuous variables and chi-square tests or Fisher's exact tests for categorical variables. This will help ensure that randomization has successfully balanced potential confounders across groups.

For the primary outcomes of average weight loss and weight gain as a proportion of birth weight, twosided independent samples t-tests will be used. The standardised effect size will be calculated using Cohen's d. A 95% confidence interval for the mean difference will be calculated. A p-value of <0.05 will be considered statistically significant. Multivariable regression analysis will be employed to adjust for potential confounders, such as birth weight, maternal age, socioeconomic status, etc. Stratified analysis will be conducted to assess the effect of KMC within each hospital. Sensitivity analysis will be conducted to assess the robustness of the results.

Analysis of secondary outcomes will be conducted based on the type of variable. For outcomes such as exclusivity of breastfeeding and perceived milk sufficiency, chi-square tests will be used, and odds ratios with 95% confidence intervals will be calculated. For outcomes measured on an ordinal scale, such as the severity of maternal depression, Kruskal-Wallis tests will be used, and cumulative odds ratios or proportional odds ratios with 95% confidence intervals will be calculated. For continuous outcomes, such as the duration of moderate to severe hypothermia, two-sided independent samples t-tests will be used, and mean differences or median differences with 95% confidence intervals will be calculated.

Masked interim analysis will be conducted for the DSMB upon completion of 50% sample size.

8.15. Monitoring & oversight

Governance & coordination:

A technical advisory group (TAG) consisting of three independent external experts will be constituted. TAG members will review the final study protocol, manual of operations, case record forms and consent forms, and may advise on practical implementation issues. They will be kept updated on the progress of the study at regular intervals. A Data Safety Monitoring Board consisting of 3-4 members will be established to monitor the trial on an ongoing basis. The DSMB will monitor the integrity of the trial and its conduct as per the study protocol and its progress as per the recruitment timeline, and assess its safety, including reviewing the incidence of SAEs.

A Steering Committee will be established, consisting of all PIs and co-PIs from the study sites. Depending upon their availability, an independent member from the ICMR child health secretariat will also be included. The steering committee will be responsible for finalizing the research protocol, manuals, CRFs, consent forms, data management, analysis plans, and interpretation and dissemination of study results.

A Trial Coordination Centre will be established at CEL, consisting of the data management team, technical expert(s), and assisted by a small team of researchers. Data from the study sites will be centrally managed, and an enrolment progress dashboard along with quality metrics with de-identified information will be reviewed during Steering Committee meetings held on a monthly basis. The Trial Coordination Centre will be responsible for the oversight of the study and in supporting the various sites in conducting research of the highest quality. Regular visits by the Trial Coordination Centre will be planned to assess the quality of the study implementation in each of the study sites and advise on study implementation, as necessary.

Study implementation teams at each site: Each site will have a screening team that will be responsible for screening every infant after birth based on their weight and other inclusion/ exclusion criteria to assess their eligibility to participate in the study, administer consent, and follow the randomized allocation procedures. A team of intervention nurses will be trained in intervention procedures and will counsel, support, supervise and keep a documented record of KMC and breastmilk feeding episodes. Each site will also have a team of independent data collectors who will collect the data on each enrolled infant at specified timepoints based on a pre-defined schedule.

8.16. Ethical considerations

8.16.1. Key Issues

The ethical considerations for this study are paramount and will be thoroughly addressed to protect the well-being and rights of the participating infants and their mothers. Informed consent will be obtained from the mothers before their inclusion in the study, ensuring that they are fully informed about the study's purpose, procedures, potential risks, and benefits. The study will be conducted in accordance with the principles of the Declaration of Helsinki and will be approved by the relevant institutional review boards or ethics committees at each participating center.

Participation in this study is completely voluntary and an informed consent will be taken, respecting participants' freedom to choose and the option to withdraw consent at any point of time without repercussions. The intervention is known to be extremely safe for preterm and low birth weight infants as well as unstable infants, and therefore expected to be safe for normal birth weight infants without complications as well. Special attention will be paid to the potential risks and discomforts associated with KMC, such as potential for hyperthermia, discomfort, or fatigue for the mother, and any potential adverse effects on the infant's health. Appropriate measures will be taken to minimize these risks, including continuous monitoring of the infant's temperature, and ensuring that the mother is comfortable and supported during KMC sessions.

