8.6. Intervention

Mother-to-newborn:

The intervention from the mother to the baby will include continuous and prolonged skin-to-skin contact (SSC) (ideally >=20 hours, but at least >=8 hours daily), along with breastfeeding on demand in the KMC position (on-demand, as initiated by the newborn as per his/her needs while in SSC) during the first 72 hours of life. Post the first 72 hours and through the newborn period, mothers will be recommended to continue with SSC as per their desire and comfort, and be advised to continue to breastfeed in the KMC position to the extent possible.

Counseling and support to the mother:

A team of lay workers trained in KMC support (called the KMC team) will be responsible for providing counselling and support to mothers on KMC during the first 48 hours of facility admission.

Mothers will be counselled on the potential benefits of Kangaroo Mother Care, and will be supported in providing prolonged KMC in the facility with the help of a binder. The KMC team will counsel and support the mother in placing the baby appropriately in skin-to-skin position, teaching her the use of binder and breastfeeding while the baby is in the KMC position. SSC during hospital stay will involve the infant and mother remaining bare-chested in the KMC position, with the baby's head covered by a cap, and feet kept warm with socks. All measures will be taken to keep the baby safe in the SSC position. This will include keeping the mother in a semi-reclined position at an angle of at 30-45 degrees (or in ambulatory position when the mother wishes) and securing the baby with a binder firmly to the chest and a shirt that provides containment in the KMC position. All routine care will be provided in SSC. Any interruptions in SSC will be documented to determine the duration for which the intervention was provided per day (dose). The KMC team will take all measures to ensure that mothers provide continuous KMC, with >= 20 hrs of daily SSC without removing the baby for breastfeeding, to the extent possible.

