Post 48 hours, the mother-baby dyad will be discharged from the facility in ambulatory KMC (provided there are no signs of complications in either mother or baby that require a longer duration of hospital stay). The KMC team will ensure that the mother-baby dyad is discharged in the KMC position along with counselling on continuing KMC similarly for at least 1 more day at home. The KMC team will remind mothers/ family members telephonically in the morning and afternoon of the day after discharge to encourage the provision of prolonged KMC (ideally >=20 hours, but at least >=8 hours). Post 72 hours, on Day 4, the KMC team will make a final call to mothers and family members to recommend them to continue keeping the baby in SSC for as long as they wish, as per their desire and comfort, and be advised to continue to breastfeed in the KMC position throughout the newborn period.

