8.7. Common minimum care package for both the study groups

Both groups will receive the standard of care as per the facility norms by facility health providers. This may include basic counselling including lactation, record-keeping, general assessment, vaccinations, etc. by the nurses and doctors in the facility.

The SESS team will strengthen the care at the study facilities, including ensuring skin-to-skin contact and breastfeeding initiation within the first golden hour with accurate measurement of the birth weight on the calibrated study weighing scale for all babies. Measures will be taken to ensure privacy for mothers and ensuring optimal ambient temperature in the labour room and wards.

The SESS team will supervise the provision of counselling on essential newborn care by facility nurse providers to ensure an equivalent counselling package to both the groups. This will include counselling on thermal care (without mentioning SSC), exclusive breastfeeding with basic lactation counselling, hygiene including handwashing and cord care, danger signs and care-seeking. Mothers in both the

groups will be provided a "baby kit", with cap, mittens, socks, blanket, diapers, and a bottle of hand sanitizer.

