	on the follow-up day 15 visit.
Outcome 5: Mother-to-infant bonding scale measured on day 29.	Description: The Mother-to-infant Bonding Scale (MIBS) The scale was developed in London and consists of 8 different self- reported feelings of mothers towards their babies, and aims to assess how often mothers experience these feelings towards their babies. Each of the 8 items is scored on a 0-3 Likert scale. The total score is calculated by adding together the scores of the 8 items. It is reverse-scored - so a low score indicates better attachment and a high score indicates worse attachment. There is a slight variation of this scale validated in the Japanese context, consisting of 10 items. We may use the latter scale, given that it is from an Asian context. The MIBS will be administered to mothers on follow-up day 29 visit.
Outcome 6: Breastfeeding	Description:
self-efficacy scale (short form) measured on day 29.	The Breastfeeding Self-Efficacy Scale-Short Form (BSES-SF) The Breastfeeding self-efficacy scale was developed to assess maternal confidence in breastfeeding to identify mothers at risk of weaning as well as evaluate the effectiveness of various interventions in supporting breastfeeding. It consists of 14 items scored on a 5- point Likert scale, where 1 indicates 'not at all confident' and 5

indicates 'always confident'. The total score is calculated by adding together the scores on all 14 items.
The BSES-SF will be administered to mothers on follow-up day 29 visit.

Other outcome measures (sub-sample)						
Mechanistic sub-study						
Duration of hypothermia (axillary temperature < 36.5°C) over the first 48 hours of life.	Description: Continuous ambulatory temperature monitoring of the newborn will be done to compare hypothermia prevalence in infants of both groups using validated sensors (device to be decided).					
This will be assessed in a sub- sample of 40 newborns each in the intervention and control groups as part of a mechanistic sub-study.	Hypothermia is classified into three grades: Mild (36.0°C – 36 .5°C), moderate (32.0°C – 35.9°C), and severe (<32.0°C) hypothermia. The total duration of time when the device records a temperature < 36.5°C will be measured over the first 48 hours for every infant.					

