8.11. Data collection

Infants will be followed up on days 1 (24 hours after birth), 2 (48 hours after birth), 4, 8, 15 and 29 for various outcomes, including vital status, weight, infant feeding practices (observation and 24-hr recall questionnaire), other care practices (24-hour recall questionnaire), etc. The IOA team responsible for conducting the data collection will be masked to the study group. There will be a pair of assessors – a male and female assessor, conducting each follow-up visit. This is because

some of the assessments, such as breastfeeding observation and maternal mental health are sensitive and require a female assessor. The male assessors have been included for logistical reasons and will focus on gender-neutral measures like anthropometry, PSBI assessment, socioeconomic status.

STUDY PERIOD									
	Screening		F	Close -out					
Timepoint	Labor	<4hr	D1	D2	D4	D8	D15	D29	
SCREENING:									
Verbal Consent & Registration	х								
Eligibility Screening		х							
Informed Written Consent		х							
Randomization & Enrolment		х							
INTERVENTION:									
Skin-to-skin contact log			х	х					
OUTCOME ASSESSMENT:									
A. Newborn weight		х	х	х	х	х	х	х	
B. PSBI Module					х	х	х	х	
C. Anthropometry Measurement (length, head circumference, MUAC)			х					х	
D. Breastfeeding Observation (BBAT)				-		х			
E. Feeding Module			х	х	х	х	х	х	
F. Newborn Care Practices (SSC)			х	х	х	х	х	х	
G. Maternal history					х				
H. Breastfeeding Experience Scale						х			
I. Maternal Depression							х		

J. Mother-infant bonding					х
K. Breastfeeding Self-Efficacy					х
L. Socio Economic Status				х	
Mechanistic sub-study* (continuous temperature + plethysmography)		~	^		

* Sub-sample of 40 infants each from intervention and control groups (Mechanistic cohort)

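### Section 8.16.1 cites continuous infant temperature monitoring against KMC risks that include hyperthermia, but the only continuous recording described covers 40 of 258 intervention infants for 48 of 72 hours and is summarised only for low temperature

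*Protocol*

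**What the plan says.** Section 8.16.1 describes the potential risks of KMC, "such as potential for hyperthermia, discomfort, or fatigue for the mother", together with possible adverse effects on the infant. The next sentence gives the mitigation: "Appropriate measures will be taken to minimize these risks, including continuous monitoring of" the infant's temperature, along with comfort and support for the mother during KMC sessions. It names no device and no subset of infants.

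Continuous temperature recording is described in one place, the mechanistic sub-study in 8.8.2: "Continuous ambulatory temperature monitoring of the newborn will be done to compare hypothermia prevalence" in the two groups, with a sensor still to be chosen. The planned measure is "The total duration of time when the device records a temperature < 36.5°C", totalled over the first 48 hours. The schedule in 8.11 confirms the size: "Sub-sample of 40 infants each from intervention and control groups (Mechanistic cohort". Section 8.14 mentions the duration of moderate to severe hypothermia as an example of a continuous outcome.

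Other safeguards are general. Section 8.6 says "All measures will be taken to keep the baby safe in the SSC position", and has the KMC team call families "telephonically in the morning and afternoon of the day after discharge". Section 8.7 includes "ensuring optimal ambient temperature in the labour room and wards" and counselling on thermal care and danger signs. Section 8.10 places newborns under round-the-clock observation by hospital staff during the postnatal stay. Section 8.16.3 commits to monitoring, documenting and dealing with unintended effects of the intervention. A temperature of 38°C or above appears only as a PSBI sign, checked at the visits on days 4, 8, 15 and 29 (8.8.2).

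**The concern.** The ethics section presents continuous temperature monitoring as a protection against a named risk. Anyone looking for how it is delivered finds one research measurement in a small subset, aimed at the opposite problem. The recording is set up to compare cold exposure between arms, and no high threshold, alert or response is attached to it.

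Two things are at stake, both modest. The first is whether an ethics committee would understand from 8.16.1 what is done for an intervention infant outside the sub-study. The second is that the trial will hold temperature traces from 40 infants in prolonged skin-to-skin contact, and the plan as written would examine them for hypothermia only. High readings in the same traces would reach the DSMB only if someone thought to ask.

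Other reporting routes do not clearly fill this gap. Reportable SAEs are newborn death and admission to a Level-2 or higher unit (8.10), so overheating managed on the ward is not reportable. The 38°C sign is first assessed on day 4, after the 72-hour intervention period.

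**Working it through.** **Inputs**
- Total sample size 516, with 129 per group in each of two facilities (8.9).
- Sub-study of 40 infants per group, recorded over the first 48 hours (8.8.2, 8.11).
- Intervention period of 72 hours, with discharge after about 48 hours and the third day at home (8.6).

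**The plan's own figure, used here only as a denominator.** With SD 3.6, difference 1.5, two-sided alpha 0.05 and 90% power, n = 2 × (1.960 + 1.282)² × 3.6² / 1.5² = 121.05, rounded up to 122. Multiplying by the design effect of 2.0 gives 244 per group, as stated. Then 122 / 0.95 = 128.4, rounded up to 129 per group per facility, and 129 × 4 = 516. Each arm has 129 × 2 = 258 infants.

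**Coverage of the described recording.** The risk in question comes from prolonged KMC, so the intervention arm is the relevant denominator.
- Intervention infants with continuous recording: 40/258 = 15.5%.
- Intervention infants with none described: 258 − 40 = 218 (84.5%).
- Share of the intervention period recorded in the 40: 48/72 = 67%. The third day, at home, is not covered.

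**Direction of the planned summaries**

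| Place | What is summarised | Side |
|---|---|---|
| 8.8.2, purpose | Hypothermia prevalence | Low |
| 8.8.2, measure | Time below 36.5°C | Low |
| 8.8.2, grades | Mild, moderate and severe hypothermia | Low |
| 8.14, example | Duration of moderate to severe hypothermia | Low |

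No entry is on the high side.

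**What a high-side summary could show.** The protocol gives no rate for readings at or above 38°C, so these figures rest on assumed rates.
- If none of 40 infants has such a reading, the one-sided 95% upper bound is 1 − 0.05^(1/40) = 7.2%.
- If a proportion p would have at least one, the chance of seeing one or more among 40 is 1 − (1 − p)^40. This is 55% for p = 2%, 87% for p = 5% and 99% for p = 10%.
- At the 50% safety review fewer traces exist. Assuming that half the sub-study is complete by then (20 per arm), the bound after no events is 1 − 0.05^(1/20) = 13.9%.

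**The case against.** The strongest reply is that 8.16.1 is a commitment about care, while 8.8.2 describes a research measurement, and nothing says that the first must be delivered by the second. Hospital staff observe all newborns during the stay (8.10), unintended effects are to be monitored (8.16.3), and the SOPs and manual of operations mentioned in 8.12 and 8.15 are not at hand. The 8.11 schedule lists trial assessments, so its lack of a temperature row for all infants on days 1 and 2 is not evidence about ward care. This stands. A reader might infer that infants outside the sub-study go without temperature checks, or that the protocol contradicts itself. The documents support neither. They show a safeguard whose delivery is not described.

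A reader might also count every infant outside the sub-study, 516 − 80 = 436, as lacking a promised protection. Half of these are controls, who are not assigned prolonged KMC. The count that bears on the named risk is 218.

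The wording leaves some room. Hyperthermia could be read as the mother's, and the closing reference to KMC sessions could limit when monitoring applies. But the measure offered is the infant's temperature, so the infant reading is the natural one.

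Finally, 8.14 is a high-level plan, hypothermia duration is only an example in it, and a descriptive safety table could properly sit in the SAP or DSMB material. A mechanistic outcome focused on cold is also a legitimate choice. Both points are fair, and the absence of such a table is not counted here as an error. The suggestion is worth making because the protocol itself names the high-side risk and temperature monitoring as its mitigation, then fixes the purpose and threshold of the only described recording on the low side.

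**Conclusion.** The point holds in a limited form. The described continuous recording reaches 40 of 258 intervention infants (15.5%) for 48 of 72 hours, and its stated summaries would not show overheating. For the remaining 218 intervention infants the protocol offers general safeguards that may include clinical temperature checks but do not state them.

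This rests on reading hyperthermia in 8.16.1 as a risk to the infant, and on the protocol alone; the SAP, SOPs and manual might supply the missing detail. It does not show that any infant is unsafe or unmonitored. No efficacy outcome, sample size, power or error rate changes. It is a low-priority improvement to safety reporting and to one sentence of the ethics section.

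**What to change.** 1. **Use the traces already planned.** Add a descriptive safety summary, by masked arm, of the number of infants with any reading at or above 38°C and the time spent there. Give it to the DSMB at the 50% safety review already planned in 8.10 and again at the end. The 38°C value is the only high threshold in the protocol; it is borrowed from a visit-based PSBI sign, so it should be labelled as descriptive.

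2. **Make 8.16.1 match what is done.** Either state how temperature is monitored in intervention infants outside the sub-study, or limit the word continuous to the sub-study and cite the safeguards in 8.6, 8.7, 8.10 and 8.16.3 for the rest. The first is preferable if ward checks are in fact made, because it keeps the commitment and explains it.

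**Cost.** One extra table, one revised sentence and an ethics resubmission under 8.16.2. No new visit or procedure is needed, provided that the sensor still to be chosen reads reliably above 38°C.

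**Limits.** Precision is low, as the 7.2% bound shows, and lower at the interim. Day 3 stays unrecorded, and so do the 218 other intervention infants. The summary describes; it is not a test of harm, and it does not replace bedside response to a hot infant.
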